5.6.2. Study Drug Dose Intensity

Actual Cumulative Dose

Actual cumulative dose is defined as the total dose of the medication given during the study treatment exposure. All doses, including unscheduled doses, will be included in the calculation.

Actual cumulative dose (mg) = sum of (actual dose * actual frequency * duration per dose)

Dose Intensity and Relative Dose Intensity

Planned dose intensity (PDI) is defined as follows:

- $PDI \text{ (mg/ day)} = \text{Assigned treatment dose arm (i.e., total dosage per day)}$

Actual dose intensity (ADI) is defined as follows:

- $ADI \text{ (mg/ day)} = \text{Actual cumulative dose (mg)} / \text{Actual duration of exposure (day)}$

Relative dose intensity (RDI) is defined as follows:

- $RDI \text{ (\%)} = (ADI / PDI) * 100$

The number and percentage of patients in the following categories for RDI will be presented for: $> 0 - < 80\%$, $80\% - 100\%$, $> 100\% - \leq 120\%$, $> 120\%$.

Percentage of Intended Dose

Percentage Intended Dose (PID) will be calculated as:

- $(\text{Actual cumulative dose} / \text{Intended cumulative dose}) * 100$

Intended cumulative dose is defined as planned dose intensity * total duration of exposure.

The number and percentage of patients in the following categories for PID will be presented for: $> 0 - < 80\%$, $80\% - 100\%$, $> 100\% - \leq 120\%$, $> 120\%$.

5.6.3. Study Drug Modification

Study drug modifications will be summarized by treatment group in the following categories: dose reduction, dose interruption, dose modification (dose reduction or dose interruption). The number of patients and percentage who had at least one of event in each category and the number of study drug modifications (0, 1, 2 etc.) will be prepared separately.

The reasons for study drug modifications as above are also summarized according to categories collected in CRF.

6. EFFICACY ANALYSIS**6.1. General Consideration of Efficacy Analysis**

ITT will be used as the primary analysis set for the primary and secondary efficacy analyses. The PPS will be used for the supportive analysis of the primary efficacy endpoint. Patients will be assigned to the treatment group which they are randomized to in Study Part 1.

Patients will be randomized according to the stratification factor of China versus non-China sites. When appropriate, the stratification factor will be included in the statistical model for efficacy analyses with the strata information as entered in IWRS at the time of randomization. All statistical tests will be two-sided at the alpha of 0.05 significance level.

The study will include three sets of planned efficacy analyses as outlined below. Detailed definitions of treatment groups refer to [Table 4.6](#).

- Primary Efficacy Analysis at the End of Study Part 1

The primary efficacy analysis by the randomized treatment groups of ABSK021 and Placebo will be performed on efficacy data up to the end of Study Part 1 with the last assessment at Week 25 visit before the first dose of Part 2. Formal statistical inferences will be generated, and results from this set of analysis will be used as the key efficacy findings of this study. See [Table 4.6](#) for details.

- Final Efficacy Analysis at the End of Study Part 2

The final efficacy analysis for ABSK021 will be performed on all efficacy data collected in Part, Part 2 and Part 3 up to the DCO.

- End of Study Efficacy Analysis at the End of Study Part 3

The long-term efficacy analysis for ABSK021 will be performed on all efficacy data collected in Parts 1 – 3.

For the primary analysis at the end of study Part 1, the baseline for an efficacy variable is the last non-missing value before randomization. In addition, baseline values for PRO variables are the mean of non-missing values within 14 days before randomization and non-missing values before the first dose of C1D1. The baseline for each PRO variable is defined in detail in their corresponding sections below. For the final analysis at the end of study part 2, for the randomized ABSK021 treatment group, the baseline will follow all baseline definitions in Part 1.

For Placebo Switched to the ABSK021 group, the baseline value will be derived from the measurement values recorded on or before the date of the first dose of ABSK021 in Part 2. Specifically, for both BIRC and Investigator's tumor assessments, a patient's last time point tumor assessment of Part 1 will be considered as the baseline for Part 2 (see details in [Section 6.5.1](#)). The last non-missing measurement recorded on or before the date of the first dose of ABSK021 in Part 2 will be used as the baseline for ROM, PROMIS-PF, and EQ-5D-5L efficacy endpoints. The average of at least 4 of 7 consecutive days before the last visit recorded on or before the date of the first dose of ABSK021 in Part 2 will be used as the baseline for BPI-Worst-Pain NRS and Worst-Stiffness-NRS. Post-baseline values will be derived as the data collected after the first dosing of ABSK021 in Part 2.

6.2. Testing Strategy and Multiplicity Adjustments

A hierarchical gatekeeping testing procedure will be applied to control family-wise Type-1 error rate at 2-sided $\alpha = 0.05$ level over the primary testing treatment effect of primary and key secondary endpoints. These five key secondary efficacy endpoints will be tested in the prespecified order below:

- 1) 25-week ORR by BIRC based on TVS
- 2) Mean change from baseline in relative ROM of the affected joint at Week 25
- 3) Mean change from baseline in Worst-Stiffness-NRS score at Week 25
- 4) Mean change from baseline in BPI-Worst-Pain-NRS score at Week 25
- 5) Mean change from baseline in PROMIS PF scale score at Week 25

The treatment effect on the second endpoint #1 can only be evaluated if the statistically significant treatment effect on the 25-Week ORR by BIRC has been established at the 2-sided significance level of 0.05 ($P < 0.05$); and the treatment effect on the second endpoint #2 will be evaluated only if the statistically significant treatment effect on the second endpoint #1 has been established at the 2-sided significance level of 0.05. Similarly, all remaining secondary endpoints can be sequentially tested at a 2-sided significance level of 0.05 in the pre-specified order. A statistical test for any subsequent secondary endpoint (s) will not be performed if the treatment effect on any preceding secondary endpoint is not statistically significant.

Once an efficacy endpoint is found to be insignificant ($P \geq 0.05$), the formal testing procedure will stop. For all subsequent key efficacy endpoints, nominal p-values will be provided but will not be considered a formal test of hypotheses. Unless otherwise stated, all statistical tests will be conducted at the 2-sided significance level of 0.05.

No multiplicity adjustments will be applied to any other analyses of efficacy endpoints. Nominal p-values may be computed for these analyses as a measure of the strength of association between the endpoint and treatment effect rather than formal tests of hypotheses, if applicable.

6.3. Primary Efficacy Analysis at the End of Study Part 1

6.3.1. Definition of Primary Efficacy Endpoint

During Study Part 1, tumor scans are scheduled on Day 1/Week 13 and Day 1/Week 25. In this randomized study, there is no requirement for a confirmation scan during the subsequent MRI assessment to determine a Complete Response (CR) or Partial Response (PR) in accordance with RECIST v1.1. A blinded independent radiology committee (BIRC) at the CRO Clario will evaluate the radiographic images and provide Time Point Response (TPR) at Week 13 and Week 25, and cross-time point assessments including the Response Status, the Date of Progression (if applicable), and the Date of First Response (if applicable) according to RECIST v1.1. Further details can be found in [Table 6.1](#) for the necessary clarifications to determine the Response Status. Details refer to the Blinded Independent Review Charter for this study.

The primary efficacy endpoint, BIRC-25-Week ORR, will be calculated as the proportion of patients classified as responders, i.e., those achieving either a Complete Response (CR) or Partial Response (PR) within 25 weeks, with all randomized patients as the denominator. The calculation will follow these rules in line with the data handling strategy for intercurrent events:

- If patients undergo dose modifications due to toxicity before the Week 25 visit, any response that occurs after the dose modification will be included in the calculation of ORR, aligning with the treatment policy strategy.
- If patients undergo treatment discontinuation without disease progression before the Week 25 visit, any response that occurs after treatment discontinuation will be included in the calculation of ORR, aligning with the treatment policy strategy.
- If patients receive an alternative anticancer therapy (including surgery) before the Week 25 visit, only responses that occurred before the event will be included in the calculation of ORR, aligning with the while-on-treatment policy strategy.

Table 6.1 Evaluation of Response Status – Part 1

TPR at Week 13	TPP at Week 25	Overall Response Status at Week 25 (i.e., BOR)
CR or PR	CR	Response (CR)
CR or PR	PD	Non-response (PD)
PR	non-CR/non-PD/non-NE	Response (PR)
SD	CR or PR	Response (CR or PR from Week 25)
SD	SD	Non-response (SD)
SD	PD	Non-response (PD)
CR, PR, SD, or NE	NE	Non-response (NE)
PD	Any	Non-response (PD)
NE	CR or PR	Response (CR or PR from Week 25)
NE	SD or PD	Non-response (SD or PD from Week 25)

TPR = time point response; CR = complete response; NE = Not evaluable (including MRI scan is not done); PD = progressive disease; PR = partial response; SD = stable disease

Statistical Analysis Plan for Protocol ABSK-021-301

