The best overall response is determined once all the data for the subject is known. Best response determination in trials where confirmation of complete or partial response IS NOT required: Best response in these trials is defined as the best response across all time points (for example, a subject who has SD at first assessment, PR at second assessment, and PD on last assessment has a best overall response of PR). When SD is believed to be best response, it

must also meet the protocol specified minimum time from baseline. If the minimum time is not met when SD is otherwise the best time point response, the subject's best response depends on the subsequent assessments. For example, a subject who has SD at first assessment, PD at second and does not meet minimum duration for SD, will have a best response of PD. The same subject lost to follow-up after the first SD assessment would be considered unevaluable.

Target Lesions	Non-target Lesions	New Lesions	Overall Response
CR	CR	No	CR
CR	NON-CR/non-PD	No	PR
CR	Not evaluated	No	PR
PR	Non-PD or not all evaluated	No	PR
SD	Non-PD or not all evaluated	No	SD
Not all evaluated	Non-PD	No	NE
PD	Any	Yes or No	PD
Any	PD	Yes or No	PD
Any	Any	Yes	PD

CR = complete response; PR = partial response; SD = stable disease; and PD = progressive disease.

Note:

When nodal disease is included in the sum of target lesions and the nodes decrease to “normal” size (<10 mm), they may still have a measurement reported on scans. This measurement should be recorded even though the nodes are normal in order not to overstate progression should it be based on increase in size of the nodes. As noted earlier, this means that subjects with CR may not have a total sum of “zero” on the eCRF.

In trials where confirmation of response is required, repeated ‘NE’ time point assessments may complicate best response determination. The analysis plan for the trial must address how missing data/assessments will be addressed in determination of response and progression. For example, in most trials it is reasonable to consider a subject with time point responses of PR-NE-PR as a confirmed response.

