a population-level summary in patients with TGCT who meet the eligibility criteria, regardless of (1) dose modifications due to toxicity or (2) early discontinuation of treatment not due to PD or (3) before receiving an alternative anti-tumor therapy (including surgery).	
Estimand Attributes	
Treatment	ABSK021 50 mg QD vs. matching placebo QD for 24 weeks
Population	Eligible TGCT patients
Variable/Endpoint	The BIRC-25-Week ORR is defined as the proportion of patients achieving a best overall response of CR or PR within 25 Weeks based on RECIST v1.1 as assessed by BIRC in Part 1.
Intercurrent events	Handling Strategy
Dose modifications (including dose interruption and dose reduction) due to toxicity	Treatment policy strategy: continue to collect and use the data even if the patient experiences the intercurrent event
Early discontinuation of treatment not due to PD	Treatment policy strategy: continue to collect and use the data even if the patient experiences the intercurrent event
Receiving an alternative anti-tumor therapy (including surgery)	While on treatment policy strategy: outcome after the event is considered irrelevant to the treatment effect. Data before the intercurrent event will be used.
Population-level summary	The mean difference (ABSK021 – Placebo) in BIRC-25-Week ORR based on RECIST v1.1.

Key Secondary Estimands

Tumor Volume Score (TVS)

Secondary Estimand 1: The BIRC-25-Week ORR based on TVS will be compared between ABSK021 and matching placebo using the mean difference (ABSK021 – Placebo) as a population-level summary in patients with TGCT who meet the eligibility criteria, regardless of (1) dose modifications due to toxicity or (2) early discontinuation of treatment not due to PD or (3) before receiving an alternative anti-tumor therapy (including surgery).

--

Statistical Analysis Plan for Protocol ABSK-021-301

Estimand Attributes	
Treatment	The same as the primary estimand
Population	The same as the primary estimand
Variable/Endpoint	The BIRC-25-Week ORR is defined as the proportion of patients achieving a best overall response of CR or PR within 25 Weeks based on TVS as assessed by BIRC in Part 1.
Intercurrent events	Handling Strategy
The same as the primary estimand.	
Population-level summary	The mean difference (ABSK021 – Placebo) in BIRC-25-Week ORR based on TVS.

Range of Motion (ROM)

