6.3.2. Handling of Dropouts and Missing Data

If patients withdraw consent from the study before the Week 25 visit, no further data will be collected, and only tumor scans up until the date of withdrawn consent will be included in the evaluation of tumor response. Missing MRI data will not be imputed. Patients with missing MRI data at the Week 25 visit will be considered as non-responders.

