6.5.1. Tumor Responses by Investigators

In addition to tumor responses by BIRC based on both RECIST v1.1 and TVS, the best overall response (BOR) based on RECIST v 1.1 will be determined programmatically using overall time point responses by investigators up until the last evaluable visit response at Day 1 of Week 25 visit prior to or on the date of (i) radiographic progression as defined by RECIST v1.1; or (ii) withdrawal of consent to obtain scans; or (iii) receiving subsequent anti-cancer therapy or surgery, whichever is earlier.

Statistical Analysis Plan for Protocol ABSK-021-301

Investigator-25-Week ORR will be calculated as the proportion of patients with either CR or PR (i.e., responders) as the response by the Investigator within 25 Weeks based on RECIST v1.1 criteria. The calculation will follow the same rule as the primary endpoint of BIRC-25-Week ORR. The response status within 25 weeks (i.e., BOR) will follow [Table 6.1](#) based on the tumor response at Week 13 and Week 25.

The number and percentage of patients in each category of BOR based on investigators' tumor assessments (CR, PR, SD, non-CR/non-PD, PD, or NE) will be presented for the ITT analysis set. The associated exact 95% two-sided CIs using Clopper-Pearson method will be computed for ORR.

Detailed tumor assessment data from investigators will be listed along with derived response for all randomized patients.

The best percent change from baseline in the sum of diameters of target lesions will be summarized using descriptive statistics (n, mean, standard deviation, median, minimum, and maximum). Additionally, the best percent change from baseline in the sum of diameters of target lesions of individual patients and BOR will be plotted by treatment groups using a waterfall plot. A swimmer plot of the overall response and treatment duration will be provided.

The Investigator-25-Week ORR based on RECIST v1.1 will be based on the ITT analysis set and analyzed using the same method as the primary endpoint.

To compare discrepancy of response assessments, a summary of concordance between the BICR and Investigator review of radiographic images will be provided.

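### For a Week 13 responder who has other anti-tumour therapy or surgery before Week 25, the plan's rules give opposite values of the primary endpoint

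*SAP*

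**What the plan says.** The primary endpoint counts as responders "those achieving either a Complete Response (CR) or Partial Response (PR) within 25 weeks, with all randomized patients as the denominator" (SAP 6.3.1). In Part 1 "tumor scans are scheduled on Day 1/Week 13 and Day 1/Week 25", so therapy started before the Week 25 visit leaves at most one scheduled post-baseline scan ahead of it.

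Two sets of provisions then apply to the same patient.

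- **Intercurrent-event rule.** SAP 6.3.1: "only responses that occurred before the event will be included in the calculation of ORR, aligning with the while-on-treatment policy strategy". The primary estimand in SAP 1.1 names a while-on-treatment strategy for alternative therapy: "Data before the intercurrent event will be used". Protocol Table 7 and section 7.4.4.1.2 name the same strategy, though they speak of data before the event where SAP 6.3.1 speaks of responses.
- **Classification rule.** SAP Table 6.1 and protocol Table 6 turn a Week 13 result of CR, PR, SD or NE with NE at Week 25 into non-response, and their footnotes count an undone MRI as NE. SAP 6.3.2 adds: "Patients with missing MRI data at the Week 25 visit will be considered as non-responders". It makes no exception for alternative therapy. Protocol 7.4.4.1.2 states the missing-scan rule in the sentence directly after the while-on-treatment rule.

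SAP 6.4.1.1 applies the same intercurrent-event rules and the same table to TVS-ORR. SAP 6.5.1 cuts the investigator's assessments at progression, withdrawal of consent to scans or "receiving subsequent anti-cancer therapy or surgery, whichever is earlier", and then derives response status from Table 6.1. SAP section 9 lists no change from the protocol that would settle the matter.

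**The concern.** Take a patient with PR at Week 13 who has surgery at Week 18. Under the intercurrent-event rule the Week 13 PR was reached before the event and counts. Under the classification rule there is no usable Week 25 result, so the patient is a non-responder. Both rules are stated for the primary endpoint and neither is given precedence.

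What is at stake is the estimand. A while-on-treatment strategy keeps a response reached before other therapy. Scoring every such patient as a non-responder makes other therapy itself a failure, which is a composite strategy. The documents declare the first and tabulate the second.

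The case is foreseen in the plan. Protocol 6.3.6 provides for surgery after premature discontinuation, including in Part 1, and stops progression follow-up at alternative therapy, so the Week 25 scan may never exist. SAP 5.5.4 plans a summary of new anti-cancer surgery. Protocol 6.3.6 also has the investigator and sponsor decide jointly whether emergency unblinding is needed before surgery in Part 1. That is one more reason to fix the rule in advance.

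The choice also carries to TVS-ORR, the first key secondary test in the hierarchy, to investigator ORR, and to which patients enter the duration-of-response analysis.

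**Working it through.** **Step 1. The possible readings, for PR at Week 13 and surgery at Week 18**

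| Reading | Week 25 scan | Status | Consequence |
|---|---|---|---|
| Intercurrent-event rule decides | Not used | Responder | Overrides Table 6.1 and SAP 6.3.2, which state no exception |
| Exclude post-event data, then apply Table 6.1 | Excluded or not done, so NE | Non-responder | No patient with other therapy before Week 25 can be a responder, so the SAP 6.3.1 rule never includes a response |
| Apply Table 6.1 to a scan taken after surgery | Used | Depends on that scan | Uses post-event data, against SAP 1.1 and protocol 7.4.4.1.2 |

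No reading satisfies all the stated provisions.

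**Step 2. The plan's own figures.** Inputs from SAP 1.3: 6% versus 40%, Fisher's exact test, two-sided 0.05, 75 evaluable patients at 2:1 (50 and 25). Exact enumeration gives 90.3% power when the one-sided p-value is doubled, which reproduces the stated 90%. The minimum-likelihood two-sided p-value gives 92.3%. For dropout, 75/(1 − 0.15) = 88.2, rounded up to 89, against about 90 planned. The conflict does not touch the sample-size figure.

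**Step 3. Effect per patient.** With 60 and 30 randomised:

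- ABSK021: 1/60 = 1.67 points of ORR.
- Placebo: 1/30 = 3.33 points of ORR.

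**Step 4. Effect on the primary test.** Planning rates give 0.40 × 60 = 24 ABSK021 responders and 0.06 × 30 = 1.8, taken as 2, placebo responders. The documents do not give the number of affected patients, so k, the number of ABSK021 responders who change status, is shown as a range:

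| k | ABSK021 responders | ORR | Fisher p against 2/30 |
|---|---|---|---|
| 0 | 24/60 | 40.0% | 0.0010 |
| 1 | 23/60 | 38.3% | 0.0012 |
| 3 | 21/60 | 35.0% | 0.0041 |
| 6 | 18/60 | 30.0% | 0.0146 |
| 9 | 15/60 | 25.0% | 0.0459 |
| 10 | 14/60 | 23.3% | 0.078 |

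The tenth reclassification is the first to lose significance. That count depends on the placebo result: starting from 24/60, it is 17 with no placebo responder, 12 with one, 10 with two and 7 with three.

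**Step 5. Effect on power at 60:30.** If a share q of ABSK021 responders changes status, the ABSK021 rate becomes 0.40 × (1 − q). Power (doubled one-sided to minimum-likelihood p-value) is 95.6–96.7% at q = 0, 93.3–95.0% at 5%, about 90–92.5% at 10% and 85.8–89.1% at 15%.

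**The case against.** The strongest reply is that the rules run in sequence: the intercurrent-event rule removes later data, and the table and missing-scan rule then classify what is left. The consecutive sentences in protocol 7.4.4.1.2 fit this, and the SAP wording can be read as an exclusion only. This reading gives one determinate, conservative value, and nothing in the text rules it out. But it leaves the SAP 6.3.1 rule with no response it could ever include, and it turns the declared strategy into a composite one. The contradiction then lies between the table and the estimand.

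The second reply is that the case is rare. Eligibility requires unresectable disease, other antitumour treatment is prohibited on study, and surgery after premature discontinuation is recommended no sooner than 3 weeks after the last dose. A patient responding at Week 13 has little reason to take this route within 12 weeks. This stands and limits the size of the point.

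Third, the central review charter was not available and may contain a rule. If so, it still has to match the SAP. Central readers are blinded and data are cleaned before unblinding, so a choice made by treatment arm is not shown.

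A reader might also infer that Table 6.1 breaks RECIST v1.1, because protocol Appendix 12.2 says of trials without confirmation: "Best response in these trials is defined as the best response across all time points". The documents do not support that. Appendix 12.2 reproduces generic guideline text, whereas Tables 6 and 6.1 are an explicit trial-specific rule, the same in both documents, and the SAP labels the table's result as the BOR. Scoring PR then PD as non-response is a stated, stricter choice.

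**Conclusion.** The conflict is real but narrow. For a patient with CR or PR at Week 13 and alternative therapy or surgery before Week 25, the declared estimand and SAP 6.3.1 point to response, while Tables 6 and 6.1, SAP 6.3.2 and protocol 7.4.4.1.2 point to non-response. All other patients are unaffected by this point.

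The size is 1.7 points of ORR per affected ABSK021 patient and 3.3 per affected placebo patient. The number affected is unknown and probably small. A reader might infer that the 25-week ORR is undefined in general, or that the primary result is at risk. Neither follows: with 24/60 against 2/30, nine reclassifications still leave p below 0.05. That margin assumes the planning rates and that only ABSK021 patients change status.

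The repair is still needed before unblinding, because the primary endpoint should have one value per patient and the table should agree with the strategy it is said to implement.

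**What to change.** Before unblinding, make the classification follow the declared while-on-treatment strategy:

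- Add to protocol Table 6 and SAP Table 6.1: CR or PR at Week 13, then alternative anti-tumour therapy (including surgery) before Week 25: Response, later scans not used.
- Add: SD or NE at Week 13, then alternative therapy before Week 25: Non-response. Protocol Table 1 also calls for an MRI at the end-of-treatment visit, for which the tables have no column; say whether such a scan counts if it precedes the therapy.
- Add the matching exception to the missing-scan rule in SAP 6.3.2 and protocol 7.4.4.1.2.
- Report the opposite rule (alternative therapy before Week 25 = non-response) as a sensitivity analysis.

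Alternatively, if non-response is intended, relabel the strategy as composite in SAP 1.1 and protocol Table 7, and correct the SAP 6.3.1 bullet.

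Apply the same choice to TVS-ORR and investigator ORR, and align the central review charter. The cost is a few lines of text and one extra ORR table, with no patients and no new data. The while-on-treatment option is the less conservative of the two; the sensitivity analysis covers that.
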